#### **8.3.5.2. Exposure During Breastfeeding**

An exposure during breastfeeding occurs if:

- A female participant is found to be breastfeeding while receiving or after discontinuing study intervention.
- A female is found to be breastfeeding while being exposed or having been exposed to study intervention (ie, environmental exposure). An example of environmental exposure during breastfeeding is a female family member or healthcare provider who reports that she is breastfeeding after having been exposed to the study intervention by inhalation or skin contact.

The investigator must report exposure during breastfeeding to Pfizer Safety within 24 hours of the investigator's awareness, irrespective of whether an SAE has occurred. The information must be reported using the CT SAE Report Form. When exposure during breastfeeding occurs in the setting of environmental exposure, the exposure information does not pertain to the participant enrolled in the study, so the information is not recorded on a CRF. However, a copy of the completed CT SAE Report Form is maintained in the investigator site file.

An exposure during breastfeeding report is not created when a Pfizer drug specifically approved for use in breastfeeding women (eg, vitamins) is administered in accord with authorized use. However, if the infant experiences an SAE associated with such a drug, the SAE is reported together with the exposure during breastfeeding.

#### **8.3.5.3. Occupational Exposure**

An occupational exposure occurs when a person receives unplanned direct contact with the study intervention, which may or may not lead to the occurrence of an AE. Such persons may include healthcare providers, family members, and other roles that are involved in the trial participant's care.

The investigator must report occupational exposure to Pfizer Safety within 24 hours of the investigator's awareness, regardless of whether there is an associated SAE. The information must be reported using the CT SAE Report Form. Since the information does not pertain to a

participant enrolled in the study, the information is not recorded on a CRF; however, a copy of the completed CT SAE Report Form is maintained in the investigator site file.

#### **8.3.6. Cardiovascular and Death Events**

Not applicable. Cardiovascular and death events will be collected as AE/SAE even though these events are manifestations of the end stage of TTR-CM.

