### 8.3. Adverse Events and Serious Adverse Events

The definitions of an AE and an SAE can be found in [Appendix 3](#).

AEs will be reported by the participant (or, when appropriate, by a caregiver, surrogate, or the participant's legally authorized representative).

The investigator and any qualified designees are responsible for detecting, documenting, and recording events that meet the definition of an AE or SAE and remain responsible to pursue and obtain adequate information both to determine the outcome and to assess whether the event meets the criteria for classification as an SAE or caused the participant to discontinue the study intervention (see [Section 7.1](#)).

Each participant legally authorized representative will be questioned about the occurrence of AEs in a nonleading manner.

In addition, the investigator may be requested by Pfizer Safety to obtain specific follow-up information in an expedited fashion.

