#### **8.3.7. Disease-Related Events and/or Disease-Related Outcomes Not Qualifying as AEs or SAEs**

Not applicable.

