### 10.3. Appendix 3: Adverse Events: Definitions and Procedures for Recording, Evaluating, Follow-up, and Reporting

#### 10.3.1. Definition of AE

##### **AE Definition**

- An AE is any untoward medical occurrence in a patient or clinical study participant, temporally associated with the use of study intervention, whether or not considered related to the study intervention.
- NOTE: An AE can therefore be any unfavorable and unintended sign (including an abnormal laboratory finding), symptom, or disease (new or exacerbated) temporally associated with the use of study intervention.

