#### **Events NOT Meeting the AE Definition**

Any clinically significant abnormal laboratory findings or other abnormal safety assessments which are associated with the underlying disease, unless judged by the investigator to be more severe than expected for the participant’s condition.

The disease/disorder being studied or expected progression, signs, or symptoms of the disease/disorder being studied, unless more severe than expected for the participant’s condition.

Medical or surgical procedure (eg, endoscopy, appendectomy): the condition that leads to the procedure is the AE.

Situations in which an untoward medical occurrence did not occur (social and/or convenience admission to a hospital).

Anticipated day-to-day fluctuations of preexisting disease(s) or condition(s) present or detected at the start of the study that do not worsen.

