#### **10.3.2. Definition of SAE**

If an event is not an AE per definition above, then it cannot be an SAE even if serious conditions are met (eg, hospitalization for signs/symptoms of the disease under study, death due to progression of disease).

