### **3. ENDPOINTS AND BASELINE VARIABLES: DEFINITIONS AND CONVENTIONS**

#### **3.1. Primary Endpoint(s)**

- Incidence of treatment-emergent adverse events

An adverse event is any untoward medical occurrence in a patient or clinical study participant, temporally associated with the use of study intervention, whether or not considered related to the study intervention. All adverse events that start after the first dosing but before or on the last dose plus the lag time (28 days) will be flagged as treatment emergent adverse events. Adverse events will be coded according to the Medical Dictionary for Regulatory Activities (MedDRA).

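### Protocol 8.3.6 records cardiovascular and death events as AE/SAE even when they are disease manifestations, Appendix 3 excludes expected progression, and no text says which prevails

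*Protocol*

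**What the plan says.** Protocol 8.3.6 opens with the words Not applicable and then sets a collection rule: "Cardiovascular and death events will be collected as AE/SAE even though these events are manifestations of the end stage of TTR-CM". The next section, 8.3.7, is headed "Disease-Related Events and/or Disease-Related Outcomes Not Qualifying as AEs or SAEs". Its body is Not applicable, so the study lists no exempt disease-related events.

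Section 8.3 opens with "The definitions of an AE and an SAE can be found in" and points to Appendix 3, with no exception for 8.3.6. Appendix 3 contains three relevant statements:

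- The general definition in 10.3.1: "An AE is any untoward medical occurrence in a patient or clinical study participant, temporally associated with the use of study intervention".
- Among the events that do not meet the AE definition: "The disease/disorder being studied or expected progression, signs, or symptoms of the disease/disorder being studied, unless more severe than expected" for the participant's condition.
- In 10.3.2: "If an event is not an AE per definition above, then it cannot be an SAE even if serious conditions are met". The examples given are "hospitalization for signs/symptoms of the disease under study, death due to progression of disease".

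SAP 3.1 repeats only the general definition ("An adverse event is any untoward medical occurrence in a patient or clinical study participant, temporally associated with the use of study intervention") and carries no progression exclusion. SAP 6.1.1 reports TEAEs by system organ class and preferred term, and the incidence of serious adverse events, under the primary endpoint.

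**The concern.** TEAE incidence is the only primary endpoint, and the disease under study is itself a cardiac disease that leads to heart failure and death (Protocol 2.2). A rule on whether disease-related cardiac events and deaths count as AEs therefore acts directly on the endpoint's inputs.

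Protocol 4.1 plans 5 to 10 sites. If some apply 8.3.6 and others apply the Appendix 3 exclusion, the SAE and cardiac rows become a mixture that depends on which passage each site read. The SAP can only tabulate what sites recorded, so its broader definition does not restore an event that was never entered as an AE. The same classification also decides whether the 24-hour SAE report in 8.3.1.1 is triggered.

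**Working it through.** **Step 1: apply each passage to the same event.**

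| Event | Under 8.3.6 | Under 10.3.1 and 10.3.2 |
|---|---|---|
| Death from expected ATTR-CM progression | AE and SAE | Not an AE, so not an SAE |
| Cardiovascular hospitalization for expected signs or symptoms | AE and SAE | Not an AE, so not an SAE |
| Cardiovascular event more severe than expected | AE | AE |
| Expected non-cardiovascular, non-fatal progression | Not addressed | Not an AE |

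Only the first two rows conflict. The edge of that set is not sharp. Section 10.3.1 counts an exacerbation of a pre-existing condition as an AE, and Appendix 7 lists ECG findings that qualify as SAEs. But the exclusion list in 10.3.1 also covers abnormal safety assessments tied to the underlying disease. Those items therefore do not settle how an expected-progression event is recorded.

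**Step 2: look for a precedence rule.** Section 8.3 gives no exception, Appendix 3 does not refer back to 8.3.6, and the SAP does not mention the conflict.

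**Step 3: reproduce the plan's own figure.** Inputs from Protocol 9.2: 80% probability, 3% incidence.

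- n = ln(1 − 0.80) / ln(1 − 0.03) = 52.84, rounded up to 53.
- Probability of at least one at n = 53: 1 − 0.97^53 = 80.1%. At n = 52 it is 79.5%.

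The figure reproduces, and nothing here changes it.

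**Step 4: illustrate under-recording at the protocol's 3%.** Let f be the fraction of occurrences recorded. Then P(at least one recorded) = 1 − (1 − 0.03f)^53. The values of f are assumptions.

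| f | Effective rate | P(at least one recorded among 53) |
|---|---|---|
| 1 | 3% | 80.1% |
| 0.75 | 2.25% | 70.1% |
| 0.5 | 1.5% | 55.1% |

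If a share s of occurrences arises at sites applying Appendix 3, and a share e of occurrences is expected progression, then f = 1 − s × e. With s = 0.5 and e = 0.5, f = 0.75. With s = 0.5 and e = 1, f = 0.5. So 55.1% is the worst case when sites with half the occurrences exclude, because it treats every occurrence as expected progression.

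**Step 5: any-TEAE incidence.** A participant leaves this numerator only if the disputed event is the sole TEAE. Assume 5% to 30% of participants have a disputed event, and 90% independently have some other TEAE. If every site excluded, the loss is 0.10 × 0.05 = 0.5 points to 0.10 × 0.30 = 3.0 points. None of these rates is in the documents.

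**The case against.** The strongest reply is that the text already resolves the matter. Section 8.3.6 is specific to this study, names these events, and answers the progression argument in its own subordinate clause. Section 8.3.7 exempts nothing. Section 8.3.3 and Appendix 3 ask for autopsy or postmortem findings after a participant's death, with no exception for progression. The opening Not applicable in 8.3.6 can be read as meaning that no special handling applies because these events go through ordinary AE/SAE collection. On this view Appendix 3 is general text that lacks a cross-reference.

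Most of that stands as evidence of intent. It does not remove the contradiction. Section 8.3 makes Appendix 3 the source of the definitions, and 10.3.2 names progression death as something that cannot be an SAE. A site applying it would be following the protocol.

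A reader might also infer that these events would be lost from the study, or that AE monitoring is their only capture after Month 12. The documents do not support that. Section 8.2.7 calls for hospitalization determination at each visit, with the reason, and the Synopsis lists the post-treatment follow-up among the scheduled visits, although the Schedule of Activities has no hospitalization or vital-status entry there. Vital status is otherwise scheduled through Month 12, Section 7.1 adds a Month 12 check for participants who stop treatment early, and death is a listed discontinuation reason in 7.2 that feeds the disposition summary in SAP 6.6.2. Many of these events are therefore captured, but outside the AE tables, and the SAP specifies no summary of hospitalizations or vital status.

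**Conclusion.** The contradiction is real and lies in current text: 8.3.6 requires events to be recorded that 10.3.1 and 10.3.2 exclude. It is limited to expected-progression cardiovascular events and deaths. The SAE rows and the cardiac system organ class and preferred-term rows are exposed. Any-TEAE incidence would probably move little. The study is descriptive with no hypothesis, so no decision rule is affected.

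The size cannot be estimated from the documents. They give no rate for such events, no split between expected and worse-than-expected progression, and no evidence of how sites read the two passages. The fall from 80.1% to 70.1% or 55.1% shows sensitivity at the protocol's own 3% and is not a forecast. A reader might be tempted to put a large percentage-point shift on SAE incidence, but that would rest wholly on assumed event rates and an assumed share of sites using Appendix 3.

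**What to change.** Reconcile 8.3.6 with 10.3.1 and 10.3.2. If 8.3.6 is the intended rule, as its wording indicates, add an exception to both Appendix 3 sections: cardiovascular and death events under 8.3.6 are recorded as AE/SAE in this study, including when they are due to ATTR-CM progression. Clarify what the opening Not applicable in 8.3.6 refers to. In the same amendment, align the Schedule of Activities with 8.2.7 on hospitalization determination at the post-treatment follow-up.

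The cost is a protocol amendment, which needs IRB/EC approval under 10.1.1. Sites that applied the Appendix 3 exclusion may have to enter events retrospectively, and the reported SAE count may rise. The sample size does not change.

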#### **8.3.7. Disease-Related Events and/or Disease-Related Outcomes Not Qualifying as AEs or SAEs**

Not applicable.

#### **8.3.8. Adverse Events of Special Interest**

Not applicable.

##### **8.3.8.1. Lack of Efficacy**

Lack of efficacy in an approved indication should be reported as an SAE to Pfizer Safety.

#### **8.3.9. Medical Device Deficiencies**

Not applicable.

##### **8.3.9.1. Time Period for Detecting Medical Device Deficiencies**

Not applicable.

##### **8.3.9.2. Follow up of Medical Device Deficiencies**

Not applicable.

##### **8.3.9.3. Prompt Reporting of Device Deficiencies to Sponsor**

Not applicable.

##### **8.3.9.4. Regulatory Reporting Requirements for Device Deficiencies**

Not applicable.

#### **8.3.10. Medication Errors**

Medication errors may result from the administration or consumption of the study intervention by the wrong participant, or at the wrong time, or at the wrong dosage strength.

Exposures to the study intervention under study may occur in clinical trial settings, such as medication errors.

Safety Event	Recorded on the CRF	Reported on the CT SAE Report Form to Pfizer Safety Within 24 Hours of Awareness
Medication errors	All (regardless of whether associated with an AE)	Only if associated with an SAE

Medication errors include:

- Medication errors involving participant exposure to the study intervention;
- Potential medication errors or uses outside of what is foreseen in the protocol that do or do not involve the study participant.

Such medication errors occurring to a study participant are to be captured on the medication error page of the CRF, which is a specific version of the AE page.

In the event of a medication dosing error, the sponsor should be notified within 24 hours.

Whether or not the medication error is accompanied by an AE, as determined by the investigator, the medication error is recorded on the medication error page of the CRF and, if applicable, any associated AE(s), serious and nonserious, are recorded on an AE page of the CRF.

Medication errors should be reported to Pfizer Safety within 24 hours on a CT SAE Report Form **only when associated with an SAE**.

#### 8.4. Treatment of Overdose

For this study, any dose of tafamidis greater than daily dose of study intervention within a 24-hour time period will be considered an overdose.

Sponsor does not recommend specific treatment for an overdose and may be used in case of doverdose.

In the event of an overdose, the investigator/treating physician should:

1. Contact the medical monitor within 24 hours.
2. Closely monitor the participant for any AEs/SAEs and laboratory abnormalities for at least 5 half-lives or 28 calendar days after the overdose of tafamidis. Closely monitor the participant for any AEs/SAEs.
3. Document the quantity of the excess dose as well as the duration of the overdose in the CRF.
4. Overdose is reportable to Safety **only when associated with an SAE**.

PFIZER CONFIDENTIAL

CT02-GSOP Clinical Protocol Template Phase 1 2 3 4 (15 May 2020)

Page 62

5. Obtain a blood sample for PK analysis within 14 days from the date of the last dose of study intervention if requested by the medical monitor (determined on a casebycase basis).

Decisions regarding dose interruptions or modifications will be made by the investigator in consultation with the medical monitor based on the clinical evaluation of the participant.

#### **8.5. Pharmacokinetics**

Blood samples of approximately 3 mL, to provide an approximately 1 mL plasma, will be collected into appropriately labeled tubes containing dipotassium ethylenediaminetetraacetic acid (K2EDTA) for measurement of plasma concentrations of tafamidis as specified in the **SoA**. Instructions for the collection and handling of biological samples will be provided in the laboratory manual. The actual date and time (24-hour clock time) of each sample will be recorded.

Samples will be used to evaluate the PK of tafamidis. Samples collected for analyses of tafamidis plasma concentration may also be used to evaluate safety or efficacy aspects related to concerns arising during or after the study, for metabolite identification and/or evaluation of the bioanalytical method.

Genetic analyses will not be performed on these plasma samples unless consent for this was included in the informed consent. Participant confidentiality will be maintained.

Samples collected for measurement of plasma concentrations of tafamidis will be analyzed using a validated analytical method in compliance with applicable standard operating procedures (SOPs).

The PK samples must be processed and shipped as indicated in the instructions provided to the investigator site to maintain sample integrity. Any deviations from the PK sample handling procedure (eg, sample collection and processing steps, interim storage or shipping conditions), including any actions taken, must be documented and reported to the sponsor. On a case-by-case basis, the sponsor may make a determination as to whether sample integrity has been compromised.

Any changes in the timing or addition of time points for any planned study assessments must be documented and approved by the relevant study team member and then archived in the sponsor and site study files, but will not constitute a protocol amendment. The IRB/EC will be informed of any safety issues that require alteration of the safety monitoring scheme or amendment of the ICD.

#### **8.6. Pharmacodynamics**

Pharmacodynamic (PD) parameters will be evaluated in this study.

## **TTR Stabilization and TTR Concentration Measurements**

One (1) dipotassium ethylenediaminetetraacetic acid (K2 EDTA) blood sample of approximate 10 mL (with exception of an additional approximate 10 mL of the pre-dose blood sample only on Day 1 for method development and validation) will be collected as specified in the [SoA](#) for measurement of TTR stabilization and TTR concentration. The actual date and time (24-hour clock time) of each sample will be recorded. Samples will be analyzed using validated analytical methods in compliance with Pfizer standard operating procedures. Detailed instructions for collection, storage, labeling, and shipment of all samples are provided in a separate study laboratory manual.

As part of understanding the PD of the study intervention, samples may be used for evaluation of the bioanalytical method. These data will not be included in the Clinical Study Report (CSR).

The PD samples must be processed and shipped as indicated in the instructions provided to the investigator site to maintain sample integrity. Any deviations from the PD sample handling procedure (eg, sample collection and processing steps, interim storage, or shipping conditions), including any actions taken, must be documented and reported to the sponsor. On a case-by-case basis, the sponsor may make a determination as to whether sample integrity has been compromised.

### **8.7. Genetics**

Genetics information will be collected in the study.

#### **8.7.1. Specified Genetics**

Blood samples of approximately 3 ml will be collected for measurement of genotyping for mutation of TTR gene at screening period for each participant.

#### **8.7.2. Banked Biospecimens for Genetics**

Not applicable.

### **8.8. Biomarkers**

Biomarkers are not evaluated in this study.

#### **8.8.1. Specified Gene Expression (RNA) Research**

Specified gene expression ribonucleic acid (RNA) research is not included in this study.

#### **8.8.2. Specified Protein Research**

Specified protein research is not included in this study.

#### **8.8.3. Specified Metabolomic Research**

Specified metabolomic research is not included in this study.

## 8.9. Health Economics

Health Economics parameters will be evaluated in this study as Patient Reported Outcomes:

Sites will be provided with an approved translated version of each paper-based questionnaire that will be required for use in the study.

### Kansas City Cardiomyopathy Questionnaire

The Kansas City Cardiomyopathy Questionnaire (KCCQ) ([Section 10.9.1](#)) (Green 2000) is a 23-item subject-completed questionnaire that assesses health status and health-related quality of life in participants with heart failure. Items assess the ability to perform activities of daily living, frequency and severity of symptoms, the impact of these symptoms, and health-related quality of life. Response options vary by question. Scoring yields scores for 6 domains (Physical limitation, Symptom stability, Symptoms, Self-efficacy, Social limitation, and Quality of life), domain summary scores (Functional summary and Clinical summary), as well as an Overall Summary score. Domain scores are transformed to a 0 to 100 range; higher scores indicate better health status. It takes approximately 4-6 minutes for a participant to complete the KCCQ. Participants will complete the KCCQ at the times listed in the [Schedule of Activities](#). In each instance of administration, the KCCQ should be completed by participants before completing the EQ-5D-5L ([Section 10.9.2](#)) and SF-12 ([Section 10.9.3](#)). The KCCQ can be found in [Section 10.9.1](#)

### EuroQoL 5 Dimensions 5 Levels (EQ-5D-5L)

The EQ-5D-5L (5 levels version) is a brief, self-administered generic health status instrument that takes about 5 minutes to complete. The instrument consists of 2 parts. In the first part, respondents are asked to rate their current health state on 5 dimensions (mobility, self-care, usual activities, pain or discomfort, and anxiety or depression) with each dimension having 3 levels of function (1=no problem, 2=some problem, and 3=extreme problem). The second part is a participant's self-rating of current health state on a Visual Analog Scale (EQ-5D VAS) with endpoints labeled 'best imaginable health state' (score of 100) and 'worst imaginable health state' (score of 0). The scores from the 5 dimensions may be used to calculate a single index value, also known as a utility score. Participants will complete the EQ-5D-5L ([Section 10.9.2](#)) at the times listed in the [Schedule of Activities](#).

Participants should complete the EQ-5D-5L after the KCCQ ([Section 10.9.1](#)). The EQ-5D-5L can be found in ([Section 10.9.2](#)).

